1.0 BACKGROUND AND RATIONALE

1.1 Background

Patients with localized ductal carcinoma in situ (DCIS) and Stage I-IIIA breast cancers are usually candidates for either breast conservation therapy (BCT: lumpectomy with radiation) or mastectomy since survival outcomes are comparable. By its very name, BCT implies superior aesthetic outcomes as breast tissue is preserved. Not surprisingly, when offered, the majority of women will choose BCT over mastectomy with reconstruction, (~65% BCT vs. 35% with mastectomy of which <30% of those receive a reconstruction).

The degree of tissue loss with BCT however falls on a spectrum that is influenced by tumor size and the variable impact of radiation therapy. Large-breasted women are able to absorb a larger absolute tumor resection than smaller breasted women due to the relative size of their breast. Further, the majority of women note that the upper-inner pole of their breast is more aesthetically relevant than other quadrants. Therefore, BCT impacting this region may create a relatively greater degree of dissatisfaction. A recent survey performed by the American Society of Plastic Surgeons found that ~ 46% of women undergoing BCT were disappointed with their results. In another survey – the Breast Cancer Treatment and Outcomes Survey – increased breast asymmetry following BCT was correlated with depressed mood and a feeling of stigmatization. In another study, tumors involving >10% of breast volume, and particularly those located in the medial breast, were associated with decreased patient satisfaction. Unfortunately, quantification of tumor: breast ratio was imprecisely calculated, and patient satisfaction was not determined by a validated, breast-specific patient reported outcomes tool in any of these studies.

While the percentage of women undergoing mastectomy with reconstruction is still under 30%, and approximately 70% are not even informed of their options, there is increasing evidence that successful reconstruction offers a clear biopsychosocial advantage. Advanced reconstructive techniques including nipple-sparing mastectomy, immediate implant reconstruction, microvascular perforator flaps and adjunctive imaging and materials technologies have significantly improved patient outcomes in terms of pain, function, patient reported satisfaction, and lowered complication rates. Compared to national trends, the rate of reconstruction following mastectomy is 59% overall at our institution. Of the remaining patients who did not undergo reconstruction following mastectomy, 60% chose not to have it and 40% had medical contraindications that precluded it as an option.

Our ability to quantify patient satisfaction has also improved with the advent of the Breast Q. This instrument represents the most comprehensive and specific quantitative method for patient self-assessment following breast surgery. Specific modules for breast reconstruction and BCT are available. The Breast Q is superior to other previously validated instruments like

the Short Form (SF-36) which provides a generic psychometric overview of patient satisfaction on an 8 point scale but lacks items specific to breast surgery. The European Organization for Research and Treatment of Cancer's Quality of Life Questionnaire Breast Cancer Module (EORTC QLQ-30 Br23) does provide a breast cancer-specific module, but evaluates overall function and does not differentiate between breast conservation therapy and reconstruction. We believe that for patients who get BCT, the relative size of the tumor and volume of its resection will profoundly impact breast symmetry and therefore impact patient reported outcomes on the Breast Q.

1.2 Rationale

This study will show that many patients currently selected for lumpectomy will have better aesthetic outcomes when mastectomy with reconstruction is chosen. While the absolute dimensions of a breast cancer are relevant to staging and treatment, tumor: breast ratio is a key factor in determining patient satisfaction with lumpectomy, and in turn should determine when a mastectomy with reconstruction should be performed to yield an optimal result. It is the relative size of the tumor and volume of its resection that will profoundly impact breast symmetry and therefore impact patient reported outcomes following BCT. Tumor: breast ratios > 0.2 will be associated with progressively poorer patient satisfaction outcomes when treated with BCT than would be provided by mastectomy with reconstruction. Tumors in the superomedial breast will be even more sensitive to tumor: breast ratio. We hypothesize that BCT will be particularly sensitive to tumor: breast ratio whereas mastectomy with reconstruction will be less dependent. The results from this study will enable plastic and oncologic surgeons to identify a new cohort of patients, previously destined for BCT, to undergo a mastectomy with reconstruction to optimize their overall satisfaction with the aesthetic outcomes with equivalent treatment of their disease.

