3.0 PATIENT SELECTION

3.1 Inclusion Criteria

- Patient must be scheduled to undergo breast conservation therapy (BCT), mastectomy or mastectomy with immediate reconstruction (defined as initiating the reconstructive process at time of mastectomy) for ductal carcinoma in situ (DCIS), lobular carcinoma in situ (LCIS), and early stage breast cancer (Clinical Stages IA-IIIB). Stage IIIB tumors are 2-5 cm with micrometastases 0.2 to 2.0 cm in lymph nodes; or 2-5 cm tumor with 1-3 positive axillary or internal mammary lymph nodes, or >5 cm with no lymph node involvement. Clinical staging, based on imaging and physical exam will be used for enrollment. Patients that are unexpectedly upstaged will be excluded at that time. For staging reference please see <http://www.cancer.gov/cancertopics/pdq/treatment/breast/patient/page2#keypoint13>.
- If multifocal/multicentric disease of the ipsilateral breast is encountered and patients are still deemed eligible for BCT or mastectomy per standard of care, then the tumor area will be calculated as the total volumes of the identified foci.
- Patient must be between 18-72 years old.
- Patient must be able to understand and willing to sign a written informed consent document.

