8.0 DATA SUBMISSION SCHEDULE

Case Report Form	Submission Schedule
Original Consent Form	Prior to registration
Eligibility Checklist RedCap Enrollment, Visit 1, Visit 2 MRI, and Visit 3 Plastics (if applicable)	Prior to surgery
RedCap Surgical Intervention	Following receipt of final operative and pathology reports
RedCap Follow-Up Forms Post-Operative Visit 1, Oncology Course, and Post-Operative Visit 2	
Group A:
 
 ○ Post-Lumpectomy 1st post-op visit before Radiotherapy (1-10 weeks after lumpectomy) ○ Post-Lumpectomy post-op visit after radiotherapy (6-18 months after radiation or the latest follow-up time point within the duration confines of our study period.) 
Group B:
 
 ○ Post-mastectomy 1st post-op visit before completion of reconstruction (1-10 weeks after mastectomy) ○ Post-mastectomy Post-op Visit after final reconstruction (3-8 months after final reconstructive procedure or the latest follow-up time point within the duration confines of our study period.) 
Group C:
 
 ○ Post-mastectomy 1st post-op visit (1-10 weeks after mastectomy) Post-mastectomy post-op visit (6-18 months after mastectomy or the latest follow-up time point within the

	duration confines of our study period.)
Unanticipated Event via HRPO	At the time of any unanticipated event
MRI T:B ratio, Breast Q-Scores, and Vectra Mammometrics	The coordinators will ensure MRI performed, Breast-Q's completed and Vectra images captured during active patient phase. MRI T:B ratio will be performed late in the active study phase to allow for a limited number of staff to perform bulk of measurements to optimize standardization. There is also a possibility the software will be upgraded to automate the T:B ratio later in the study period. Breast-Q scores and Vectra mammometrics will be also evaluated in bulk late in the active study phase using SAS, SPSS, or another similar statistical program.

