10.4 Sample Size

Mammometrics will be converted to comparable data and then related to Q-Score as these are expected to be complex relationships.

We anticipate enrolling 83 subjects per study arm (166 total) with up to an additional 20 subjects undergoing mastectomy without reconstruction as a negative control for a total of 186 patients.

Initial plan is to use G*Power v 3.1, or a comparable statistical package. Based on an effect size $d=0.45$, Type I error $\alpha=0.05$, and power $(1-\beta) =0.8$, normal distribution, and 2-tails, we will require 83 subjects per arm (166 total). Assumptions: A difference in mean scores of 10 on a 100-point scale (Q-Score generated from Breast Q) was assumed to be significant. This is determined by assuming an SD of 20, with one-half of an SD being the threshold of discrimination for change in health-related quality of life.

Sample size calculations are based on 1) previously reported sample size calculations where data from the Breast Q for Breast Reconstruction was used with 2) the open-source statistical package G*Power 3.1.

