10.5 Data Analysis

This is a longitudinal observational study to compare effects of two treatment groups on the quality of life and to explore how the treatment effects are modified by T:B ratio. For each study patient, we have a data vector $D=(\text{group}, \text{T:B ratio}, \text{location}, Q(t), 3D(t), W)$, where group is a binary indicator for two comparison groups. T:B ratio is the tumor: breast ratio measured at a continuous scale, and location is a binary indicator of tumor location. $Q(t)$ and $3D(t)$ are Q score and the VECTRA 3D generated mammometrics respectively, measured as continuous variables at $t=(0,1,2)$, where $t=0$ is the pre-treatment baseline measurement. W is a set of patient characteristics – e.g., age, obesity, stage, etc. A longitudinal study generates correlations among the repeated measurements within the same individual, and observational study often comes with a biased estimate of the treatment comparison due to confounding. These two issues, the correlation of repeated measurements and confounding, must be taken into account in the data

analysis. Regression analyses of correlated data can simultaneously address these two issues. There are two families of statistical methods for regression analyses of correlated data – mixed effect model and generalized estimating equation (GEE). Both are appropriate for our study, even though the interpretations are different – population average vs subject specific. Data analyses for our study will be performed within this framework to adjust for the patient characteristics for unbiased comparison of treatment effect and to take into account the correlations.

10.5.1 Primary objectives:

For main effect of treatment group on Q-score: fit and test a model with Q score as the dependent variable and group as the independent variable, controlling for W in the model – (Model 1).

For the difference in Q score between two treatment groups modified by T:B ratio: fit and test a model with Q score as the dependent variable, and group, T:B ratio, and group-by-T:B ratio interaction as the independent variables, controlling for W in the model – (Model 2). The results can be better presented as a graph with two lines – Q score as a function of T:B ratio for those treated with BCT, and for those treated with Mastectomy+reconstruction.

10.5.2 Secondary objectives:

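### The T:B threshold that answers the primary objective has no interval, no limit to ratios seen in both arms, and no check that BCT patients with high ratios are enrolled

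*Combined protocol and SAP*

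**What the plan says.** - Section 2.1 poses the primary question as a threshold: the T:B ratio at which patient-reported outcomes justify mastectomy with reconstruction over BCT. It names no value and does not define what counts as justified.
- Section 1.2 gives the expectation: "Tumor: breast ratios > 0.2 will be associated with progressively poorer patient satisfaction outcomes when treated with BCT". It adds that reconstruction should depend less on the ratio, and that the results should identify a new group of patients to move from BCT to mastectomy with reconstruction.
- Section 10.5.1 (Model 2) regresses Q score on group, T:B and their product, controlling for patient characteristics. On reporting it says: "The results can be better presented as a graph with two lines", one line per treatment.
- T:B is a volume ratio. Sections 2.2 and 6.2 derive it from 3D renderings of the MRI, and for multifocal disease 3.1 says "then the tumor area will be calculated as the total volumes of the identified foci".
- Section 10.3 deliberately includes tumours over 5 cm that are candidates for either operation. Section 6.7 describes an observational study of uninfluenced care, and no enrolment target by T:B is set.
- Section 8.0 states: "MRI T:B ratio will be performed late in the active study phase". The reason given is standardisation by a small number of staff.
- Section 10.4 sizes the study at 83 per arm for a difference in mean Q score between groups, not for the interaction or the threshold.

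**The concern.** A threshold read from two fitted lines is only as good as the data in both arms around the point where they meet. T:B rises with the cube of tumour diameter, so ratios near 0.2 need large or multiple tumours, or small breasts. The plan does nothing to secure such patients in the BCT arm and does not check whether they are there. If they are scarce, the meeting point is set mainly by the slope among small ratios and carried outward.

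Even if they are enrolled, the meeting point is a ratio of two estimated coefficients and can be very imprecise. The plan asks for no interval, so a reader of the graph could not tell a supported threshold from an unsupported one. Section 1.2 intends the result to move patients from BCT to mastectomy, so the difference matters.

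**Working it through.** **1. The plan's own figure.** For d = 0.45, two-sided alpha 0.05 and power 0.80, the normal approximation gives 78 per arm and the t test 79. A Wilcoxon-Mann-Whitney test with a normal parent distribution gives 83, so the stated number is reproducible under that variant, although 10.4 names no test. (The stated 10 points over SD 20 is d = 0.50, which is a separate matter.) No figure in the documents covers the T:B distribution or the threshold.

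**2. Geometry, without distributional assumptions.** For a single spherical focus of diameter D cm, V = (π/6)D³ mL and T:B = V / breast volume.
- D = 5: V = 65.4 mL. T:B exceeds 0.2 only if breast volume is below 65.4 / 0.2 = 327 mL.
- D = 2: V = 4.2 mL. The limit is 4.2 / 0.2 = 21 mL.
- In a 500 mL breast, 2 to 5 cm gives 4.2 / 500 = 0.008 to 65.4 / 500 = 0.13.
- The diameter needed for 0.2 is 4.9 cm at 300 mL, 5.8 cm at 500 mL, 6.7 cm at 800 mL and 7.3 cm at 1000 mL.

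**3. How many BCT patients exceed 0.2?** The documents give no sizes or breast volumes, so this is assumption: log-normal diameter (median 1.5 to 3.5 cm) and breast volume (median 400 to 800 mL), log-SD 0.5 each. Then log T:B is normal with SD √(9 × 0.25 + 0.25) = 1.58. With medians of 3 cm and 600 mL, the median ratio is 14.1 / 600 = 0.024, z = ln(0.2 / 0.024) / 1.58 ≈ 1.35, the tail is 0.088, and 83 × 0.088 = 7.3 patients. Over the grid:
- lowest (1.5 cm, 800 mL): 0.2 of 83
- median 2 cm: 0.9 to 2.6
- median 3 cm: 5.2 to 11.3
- highest (3.5 cm, 400 mL): about 17

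**4. Precision of the crossing.** At given covariates the fitted group difference is b_G + b_I × r, which is zero at r* = −b_G / b_I. The 95% Fieller interval for r* is finite only when |b_I| / SE(b_I) exceeds 1.96. Simulation inputs from 10.4: SD 20 and 83 per arm. Assumed inputs: true crossing 0.2, flat reconstruction line, reconstruction-arm median diameter 3 cm, log-SDs as above, ratios capped at 0.8, one score per patient, no covariates, 2000 trials per row. BCT slopes of 50 and 100 points per unit T:B correspond to a BCT advantage of 10 and 20 points at T:B = 0 (0.2 × 50 and 0.2 × 100).

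| BCT median diameter, breast volume | Slope | Mean BCT patients > 0.2 | Central 95% of estimated crossing | Crossing outside BCT range | Finite interval |
|---|---|---|---|---|---|
| 1.5 cm, 600 mL | 50 | 0.3 | −1.1 to 1.21 | 55% | 10% |
| 1.5 cm, 600 mL | 100 | 0.3 | −1.6 to 1.64 | 62% | 22% |
| 2 cm, 600 mL | 50 | 1.4 | −1.5 to 1.59 | 38% | 20% |
| 2 cm, 600 mL | 100 | 1.4 | −0.47 to 1.15 | 27% | 56% |
| 2.5 cm, 600 mL | 50 | 3.6 | −0.91 to 1.26 | 17% | 35% |
| 2.5 cm, 600 mL | 100 | 3.7 | 0.12 to 0.47 | 7% | 83% |
| 3 cm, 600 mL | 50 | 7.4 | 0.00 to 1.00 | 7% | 51% |
| 3 cm, 600 mL | 100 | 7.4 | 0.13 to 0.37 | 1% | 94% |
| 3 cm, 400 mL | 50 | 11.2 | 0.07 to 0.63 | 3% | 71% |
| 3 cm, 400 mL | 100 | 11.3 | 0.14 to 0.30 | 0% | 100% |

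The fifth column partly reflects the choice of 0.2 as the true crossing: where BCT data stop short of 0.2, even an exact estimate counts as outside. The last column is the more informative. It is below 80% in seven of ten rows, including the row with 7.4 BCT patients above 0.2 and slope 50.

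**The case against.** A reader might infer from the geometry that hardly any BCT patient could exceed 0.2, and hence that the reported threshold would mostly be extrapolated. The documents do not support that. They give no size or breast-volume distribution, they include BCT candidates with tumours over 5 cm on purpose (10.3), and they sum multifocal volumes (3.1), which raises the ratio. The 2 to 5 cm band in 3.1 describes only the most advanced eligible stage. The assumed counts range too widely, from under 1 to about 17 of 83, to settle the matter.

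Nor is the objective tied to 0.2. Section 2.1 leaves the ratio open, and 1.1 cites lower satisfaction for tumours above 10% of breast volume, so the crossing may lie where data are plentiful. Section 10.5.1 does not say that the lines will be projected beyond the data or that a crossing will be reported as a number. Covariates and repeated measures could make Model 2 more precise than the simulation. Late T:B measurement has a stated reason, and this point does not ask for it to change.

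All of this stands, and it limits the claim to a risk. It does not fill the gap: including large tumours shows intent but does not ensure overlap between the arms, and a two-line graph without an interval or range limit does not answer a threshold question.

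**Conclusion.** The point holds as a gap in the primary analysis. The objective asks for a threshold; the analysis gives an interaction test and a graph, with no estimator, no interval, no overlap check and no limit to shared ratios. The geometry is firm for a single spherical focus: ratios above 0.2 depend on tumours over 5 cm, multifocal disease or small breasts. How many BCT patients fall there is unknown. The imprecision rests on SD 20 and 83 per arm from 10.4 plus assumed distributions and slopes; under these, a finite interval arose in 10% to 100% of trials, and in under 80% in seven of ten scenarios. Extrapolation may or may not occur, but as written the plan would not reveal it.

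**What to change.** In 10.5.1:
- Define the threshold as the T:B value at which the fitted group difference is zero, and estimate it with a 95% confidence interval (for example Fieller or bootstrap).
- Draw the two lines and report the threshold only over T:B values observed in both arms.
- Tabulate T:B by arm, with the number of patients above 0.1 and above 0.2.
- Allow as a primary conclusion that no threshold was identified within the observed range.
- Make no claim about ratios above 0.2 if Group A has too few patients there.

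This costs a few sentences of analysis text and one table; recruitment, measurement and care do not change. The downside is that the study may have to report that no threshold could be identified.

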2.0 OBJECTIVES

2.1 Primary Objective

- At which tumor: breast ratio do patient reported outcomes justify performance of a mastectomy with reconstruction versus BCT in stage-matched patients?

2.2 Secondary Objectives

- Does tumor location impact the influence of tumor: breast ratio on patient reported outcomes following mastectomy with reconstruction or BCT?
- How does the pre and post-op Breast Q for the two groups (mastectomy + recon vs. BCT) reflect the tumor: breast ratio as calculated from 3D images rendered from MRI utilizing software-based algorithms?
- How does the pre and post-op Breast Q for the two groups (mastectomy + recon vs. BCT) reflect the VECTRA 3D generated mammometrics?

- What is the impact of radiation in BCT on Breast Q (Q-score before and after radiotherapy) and VECTRA (breast volume, nipple position, total breast skin surface area before and after radiotherapy)?
- How do complications that arise from each scenario (mastectomy + recon) vs. BCT impact patient satisfaction?
- What is the impact of tumor location and obesity as independent determinants of patient satisfaction in the two groups (mastectomy + recon vs. BCT) relative to tumor: breast ratio?

3.0 PATIENT SELECTION

3.1 Inclusion Criteria

- Patient must be scheduled to undergo breast conservation therapy (BCT), mastectomy or mastectomy with immediate reconstruction (defined as initiating the reconstructive process at time of mastectomy) for ductal carcinoma in situ (DCIS), lobular carcinoma in situ (LCIS), and early stage breast cancer (Clinical Stages IA-IIIB). Stage IIIB tumors are 2-5 cm with micrometastases 0.2 to 2.0 cm in lymph nodes; or 2-5 cm tumor with 1-3 positive axillary or internal mammary lymph nodes, or >5 cm with no lymph node involvement. Clinical staging, based on imaging and physical exam will be used for enrollment. Patients that are unexpectedly upstaged will be excluded at that time. For staging reference please see <http://www.cancer.gov/cancertopics/pdq/treatment/breast/patient/page2#keypoint13>.
- If multifocal/multicentric disease of the ipsilateral breast is encountered and patients are still deemed eligible for BCT or mastectomy per standard of care, then the tumor area will be calculated as the total volumes of the identified foci.
- Patient must be between 18-72 years old.
- Patient must be able to understand and willing to sign a written informed consent document.

3.2 Exclusion Criteria

- Cognitive impairment
- History of radiation to the chest wall or breasts
- Patients unable to undergo MRI due to metallic implant or claustrophobia
- Patients that are pregnant since breast MRI is contraindicated
- History of previous breast surgery other than primary cosmetic augmentation or breast reduction
- Identification of a concurrent or synchronous contralateral cancer during the enrollment period
- Any patient that would not have been considered for BCT or reconstruction
- BCT patients planning to proceed with reconstruction during their study participation timeline.

3.3 Inclusion of Women and Minorities

Only women will be enrolled due to the anatomical specificity of breast cancer. Members of all races and ethnic groups are eligible for this trial.

4.0 CONFIRMATION OF PATIENT ELIGIBILITY

The following information is required to confirm patient eligibility prior to registering patient:

1. Completed eligibility checklist, signed and dated by a member of the study team
2. Copy of appropriate source documentation confirming patient eligibility
3. Signed consent form
4. Documentation of informed consent process
5. Patient's race, sex, and DOB
6. Assignment of unique study identifier
7. Registering MD's name
8. Planned date of enrollment

